6.5. Scan Evaluable Population

The Scan Evaluable Population (SEP) will be defined as all subjects who receive at least one dose of INT230-6, have a baseline tumor assessment with measurable disease, and at least one on-treatment tumor evaluation via a scan at two months or later post first dose.

6.6. Exploratory Biomarker (Immune Function and others) Population

All subjects who receive at least one dose of INT230-6, have a pre-dose and at least one post-dose measurement for a specific marker will be included in the data set for that marker. All treated subjects with at least one baseline measurement will be included in predictive analyses; treated subjects with baseline measurement and at least one on treatment measurement will be included in pharmacodynamic assessments. Blood biomarker sampling was eliminated in Protocol Amendment 6. Biomarker analysis will be presented separately as an addendum.

6.7. Retreatment Population

For Cohorts A1, B1, EA, EC, EC2, and DEC, those subjects who have completed treatment and have not started on any subsequent anti-cancer therapy will be eligible for retreatment. Prior to Study Protocol Amendment 5, three subjects had initiated retreatment. This population assignment will no longer be applicable moving forward with the study. Given the few numbers, these three subjects will be described in the Clinical Study Report (CSR) with regards to safety and efficacy in the form of a case series and will also be included in summaries regarding their initial and subsequent treatment as applicable. No aggregate tables will be developed solely for this population.

7. GENERAL STATISTICAL CONSIDERATIONS

All analyses described below will be carried out using SAS® Version 9.4 or higher. Continuous variables (e.g., age) are summarized using descriptive statistics. Categorical variables (e.g., race) are summarized using counts and percentages. Percentages are calculated using the total number of subjects in each cohort.

7.1. General Reporting Conventions

In this document, when describing tables to be generated, cohort groups will be referenced as being presented ‘by treatment’. The following data conventions are applied to all data presentations and summaries.

Treatments

- Cohorts A, B1, EA, EC are to be combined for analysis and defined as low loading monotherapy treatment, where low loading refers to a lesser potential for proper treatment of a subject’s total tumor burden due to dose volume restrictions on INT230-6 during escalation.
- Cohorts EC2 and EC3 are to be combined for analysis purposes and defined as high loading monotherapy treatment, where high loading refers to a greater potential for proper treatment of a subject’s total tumor burden due to meaningfully higher dose volume amounts allowed for INT230-6.
- Cohorts DEC and DEC2 are to be combined to define INT230-6 with pembrolizumab treatment
- Cohort FEC is defined as the combination of INT230-6 with ipilimumab treatment.
 - Data will be described and summarized separately for low and high dose monotherapy cohort groups (A1/B1/EA/EC vs. EC2/EC3) and combination cohorts by treatment (DEC/DEC2 and FEC).
 - For assessments performed at defined time points, the data will be summarized and reported for each time point.
 - Summary tables for continuous variables will contain the following statistics: N (number of subjects in the population); n (number of subjects with data); mean; standard deviation (SD); median; minimum; and maximum; 25th and 75th percentiles when applicable. Selected statistics may also include a 2-sided 95% normal approximation confidence intervals (CIs) on the mean.
 - Summary tables for categorical variables will include: N (number of subjects in the denominator); n (number of subjects in the numerator); and percent and will be presented in the format XX (XX.X%), where the percentage is in parentheses. Selected statistics also may include 2-sided 95% CIs for the percent based on the exact Clopper-Pearson methodology for binomial proportions.
 - Unless noted to the contrary, the denominator used for the calculation of percentages will be the number of subjects in the specified analysis population who are in the cohort being summarized.
 - Date variables are formatted as yyyy-MM-dd for presentation. Time is formatted in military time as HH:MM for presentation.
 - The baseline value for a given parameter is the last non-missing value prior to the first dose. A value is considered to be post-baseline if it is obtained after the first study drug administration.

- Change from baseline is calculated as (post-baseline result – baseline result). Percent change from baseline is calculated as (change from baseline/baseline results * 100). If either the baseline or post-baseline result is missing, the change from baseline and/or percent change from baseline is set to missing as well.
- Data from study centers will be pooled for all analyses
- Study Day is defined as calendar date – date of first treatment + 1 if the calendar date is on or after the date of first treatment, and calendar date – date of first treatment if the calendar date is before the date of first treatment
- Measurements from unscheduled visits will be included in listings, but not summary tables
- Missing data conventions for individual endpoints are described in detail below for the endpoints
- Listings will be provided of all data collected in the electronic Case Report Form (eCRF)
- Wherever possible, data will be decimal aligned
- For continuous variables, use the following conventions for significant digits: mean (xx.x), median (xx.x), standard deviation (xx.xx), minimum (xx.x) and maximum (xx.x). If data results are less than 1, format decimal points to one more place than the measured value for all summary variables except format to two more places for standard deviations
- Version 25.1 of MedDRA will be used for this study.
- WHODRUG Enhanced Sep-2022 B3 will be used for this study.

The accompanying table, listing, figures (TLF) document to this SAP provides the expected layout and titles of the tables, figures, and listings. Any changes to format, layout, titles, numbering, or any other minor deviation will not necessitate a revision to the SAP nor will it be considered a deviation from planned analyses. Only true differences in the analysis methods or data handling will necessitate such documentation. Please refer to the SAP appendix for additional programming notes.

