For DCR in each expansion cohort, an exact binomial 95% confidence interval will be determined by Clopper-Pearson method. Median time to response and duration of response will be summarized for those subjects with confirmed responses, using Kaplan-Meier method; PFS will be similarly summarized. Individual tumor measurements, tumor burden and % changes in tumor burden will be listed. Changes in tumor burden will be presented graphically.

With 16 subjects treated in an expansion cohort, at a fixed dose and tumor type, the 90% confidence interval for a disease control rate would be (3.4% to 36%) if 2 subjects (12.5%) had a response, (5.3% to 42%) if 3 (19%) subjects had a response, (9.0% to 48%) if 4 (25%) subjects had a response, and (13.2% to 54.8%) if 5 (31%) subjects had a response.

Pharmacokinetic Analyses:

A final PK analysis section will be included in the final clinical study report. The release kinetics of each analyte is not expected to be uniform across subjects. Sponsor shall assess the blood concentrations of the three analytes for each subject at the first cycle. Sponsor shall correlate the systemic measurement (Cmax, AUC) of the 3 analytes to measured markers of systemic toxicity (in particular renal and blood – the known toxicities of the two active agents; cisplatin & vinblastine). Human plasma will be analyzed for the concentration of vinblastine and SHAO using validated LC/MS/MS methods, and for cisplatin using a validated ICP-MS method. For pharmacokinetic profiling platinum drugs, total platinum levels in subject plasma or urine are routinely determined by spectroscopy methods as a surrogate. Thus an ICP-MS method will be developed for this study to measure total platinum in human samples as a surrogate for cisplatin.

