14.2.5. Exploratory Biomarker (Immune Function and others) Data Set

All subjects who receive at least one dose of INT230-6 and have at least one measurement for a specific marker will be included in the data set for that marker. All treated subjects with at least one baseline measurement will be included in predictive analyses; treated subjects with baseline measurement and at least one on treatment measurement will be included in pharmacodynamic assessments. Blood biomarker sampling has been eliminated in Amendment 6.

14.2.6. **Retreatment Population**

For cohorts A1, B1, EA, EC, EC2, DEC, those subjects who have completed treatment and have not started any subsequent anti-cancer therapy were eligible for retreatment. Subjects who qualified for re-initiation of treatment were evaluated for safety and efficacy based on availability of data.

14.3. **Statistical Considerations**

Please refer to the Statistical Analysis Plan (SAP).

14.3.1. **Demographics and Baseline Characteristics**

Subject demographics and baseline characteristics including age, sex, race, ethnicity, weight, baseline disease diagnosis, and medical conditions will be summarized by dose level using descriptive statistics.

14.3.2. **Extent of Exposure**

The dose of INT230-6 taken by subjects will be summarized by total dose and number of tumors injected. Additional parameters will be summarized, such a reason for study drug interruption and number of tumors with drug exuded. A by-subject listing of treatment exposure will be generated.

Combination study drugs for cohorts 7 and higher will also be summarized. Details will be provided in the statistical analysis plan.

14.3.3. **Tumor Response.**

The primary efficacy endpoint of disease control rate (DCR), defined as the sum of complete, partial and stable disease responses divided by the total number of subjects in the efficacy population, will be determined per iRECIST criteria for fixed dose and expansion cohorts. DCR will be tabulated by overall and by tumor type. Exploratory analysis will be conducted by cohort, Phase 1 cohorts (monotherapy and PD-1), Phase 2 cohorts (monotherapy, PD-1 and CTLA-4), Phase 1 and 2 cohorts (monotherapy and PD-1), tumor types, study visit, number of INT230-6 doses, number of cycles of INT230-6 (i.e., retreatment), and number of prior lines of therapy. Since iRECIST methods were not implemented at the time of dose escalation, DCR for these cohorts will be analyzed per RECIST v1.1.

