DEC	Dose Escalation, Combination Therapy	PRIMARY	Assess the safety and tolerability of INT230-6 with pembrolizumab	Grade 3, 4, or 5 study drug-related adverse events attributed to the combination and not the underlying disease
		SECONDARY	1) Characterize the overall safety of INT230-6 combined with pembrolizumab 2) Assess the injected tumor response 3) Characterize the pharmacokinetic profile of multiple doses of the three INT230-6 components (CIS, VBL, and SHAO) after single and then multiple IT tumor site injections.	1) Incidence and severity of treatment-emergent adverse events (TEAEs) Clinical laboratory results (hematology, chemistry, urinalysis) ECOG performance status Physical examination, including vital sign measurements ECG results 2) Injected Response Rates 3) C_{\max} , C_{\min} , T_{\max} , AUC_{TAU} , Accumulation index
		EXPLORATORY	1) Characterize tumor response in injected and non-injected sites 2) Evaluate various tumor and anti-tumor immune response biomarkers that may correlate with tumor response 3) Characterize the pharmacodynamics (PD) profile of the INT230-6 plus pembrolizumab in subject blood and in treated and untreated tumors 4) Assess the overall survival in subjects receiving INT230-6 plus pembrolizumab meeting inclusion criteria.	1) Bystander Response Rates, Objective Response Rates, Best Overall Response, Duration of Response 2) Biomarker results 3) PD profile results 4) PFS and OS as defined in Section 9.2 of this document
DEC2	Highest INT230-6 Dose, Combination Therapy	PRIMARY	Preliminary efficacy of INT230-6 combined with pembrolizumab	Disease control rate (CR + PR + SD) of multiple intratumoral doses of INT230-6 combined with pembrolizumab and assessed with criteria based on RECIST or iRECIST
		SECONDARY	1) Characterize the overall safety of INT230-	1) Grade 3 or higher adverse events attributed to the

Cohort	Cohort Description	Number	Objective	Endpoint

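### The SAP pools DEC with DEC2 for reporting and specifies no DEC2-only disease control rate, although DCR is DEC2's primary endpoint

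*SAP*

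**What the plan says.** SAP 7.1 opens its list of rules with "The following data conventions are applied to all data presentations and summaries". Among them are "Cohorts DEC and DEC2 are to be combined to define INT230-6 with pembrolizumab treatment" and "Cohorts EC2 and EC3 are to be combined for analysis purposes and defined as high loading monotherapy treatment". FEC is kept as a group of its own.

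SAP Table 2 sets endpoints cohort by cohort. For DEC2 the primary objective is "Preliminary efficacy of INT230-6 combined with pembrolizumab", and the primary endpoint is "Disease control rate (CR + PR + SD) of multiple intratumoral doses of INT230-6 combined with pembrolizumab". For DEC the primary endpoint is "Grade 3, 4, or 5 study drug-related adverse events attributed to the combination and not the underlying disease", and Table 2 does not list DCR for DEC at any level. EC3 takes the objectives of the escalation monotherapy cohorts, so its primary endpoint is safety and DCR is secondary.

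SAP 9 says that efficacy data are shown by treatment, with subgroups where indicated. It then says that DCR is given with exact 95% intervals by study part, in three populations, and by subgroup.

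The protocol synopsis states: "For DCR in each expansion cohort, an exact binomial 95% confidence interval will be determined by Clopper-Pearson method". Protocol 14.3.3 lists exploratory DCR analyses by cohort, for Phase 1, for Phase 2 (monotherapy, PD-1 and CTLA-4 separately) and for the two phases together. SAP 13 records no changes from the protocol's statistical methods.

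**The concern.** DEC and DEC2 were set up to answer different questions. DEC gave escalating INT230-6 with pembrolizumab, included a lead-in restricted to superficial tumors, and allowed retreatment. DEC2 gave INT230-6 up to a 175 mL maximum, followed by maintenance every 9 weeks. A DCR over both cohorts is a weighted average of two regimens, with weights set by how many subjects happened to enroll in each.

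If the SAP 7.1 groups are followed as written, the result reported against DEC2's primary endpoint includes subjects from an escalation cohort for which Table 2 names no DCR endpoint. What is at stake is the interpretation of a named primary endpoint, and whether a reader can tell which regimen the estimate describes.

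**Working it through.** **Step 1. Which DCR rows does the SAP define?**

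| Rule | Source | Row that contains DEC2 |
|---|---|---|
| By treatment | SAP 7.1, SAP 9 | DEC + DEC2 |
| By study part alone | SAP 9, with the Study Part column of SAP Table 3 | EC3 + DEC2 + FEC |
| By subgroup | SAP 7.5 | None is defined by cohort |
| Study part crossed with treatment | Not stated | DEC2 alone |

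The SAP gives no definition of study part other than that column of Table 3, which has two levels: Escalation (A1, B1, EA, EC, EC2, DEC) and Phase 2 (EC3, DEC2, FEC). SAP 4.5 makes a similar two-way split for protocol deviations. Taken alone, the Phase 2 level mixes monotherapy, pembrolizumab and ipilimumab subjects. Only the crossed reading isolates DEC2.

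**Step 2. The plan's own precision figures.** SAP 5 gives 90% intervals for 16 subjects. Two-sided 90% Clopper-Pearson limits are:

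- 3/16: 5.3% to 41.7% (SAP: 5.3% to 42%)
- 4/16: 9.0% to 48.4% (SAP: 9.0% to 48%)
- 5/16: 13.2% to 54.8% (SAP: 13.2% to 54.8%)

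These reproduce, so there is no arithmetic error here. The SAP gives no power calculation or hypothesis test for DCR.

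**Step 3. How far can pooling move the estimate?** With d the DCR of DEC minus that of DEC2:

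pooled DCR − DEC2 DCR = d × n(DEC) / [n(DEC) + n(DEC2)]

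Sizes are assumptions, because the documents give no enrollment by cohort. DEC is taken as 6 to 12, from the 6+6 design in SAP 4.1.1. DEC2 is taken as 10 to 44: 10 is the lower end of the expansion size in SAP 4.1.3, and 44 is the maximum in SAP 4.1.2.

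| Size of d | Smallest shift (6 with 44) | Largest shift (12 with 10) |
|---|---|---|
| 10 points | 10 × 6/50 = 1.2 | 10 × 12/22 = 5.5 |
| 20 points | 20 × 6/50 = 2.4 | 20 × 12/22 = 10.9 |
| 30 points | 30 × 6/50 = 3.6 | 30 × 12/22 = 16.4 |

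The shift takes the sign of d, so it can flatter DEC2 or count against it.

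**Step 4. What would a DEC2-only interval look like?** At an assumed DCR of 50%, the exact 95% limits are:

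- 5/10: 18.7% to 81.3%
- 8/16: 24.7% to 75.3%
- 22/44: 34.6% to 65.4%

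As an illustration, take 8/16 in DEC2. Adding 4/12 from DEC gives 12/28 = 42.9% (24.5% to 62.8%). Adding 8/12 instead gives 16/28 = 57.1% (37.2% to 75.5%). In the first case the interval narrows from 50.6 to 38.3 points wide, but it no longer describes DEC2.

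**The case against.** The strongest reply is that SAP 9 already asks for DCR by study part. Crossed with treatment, that yields DEC2 alone and EC3 alone. Protocol 14.3.3 plans DCR by cohort and for Phase 2 PD-1, SAP 13 claims no departure, and the table layouts sit in a shells document that is not available. A reader might infer from SAP 7.1 that DEC2's DCR will be analyzed only in the pool and never shown by itself. The documents do not support that: the crossed reading is possible, and a DEC2 table may exist in the shells. What remains is that the SAP never states the crossing, and its explicit reporting rule points to the pool.

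Other points that stand against a wider claim:

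- **EC3.** A reader might infer that pooling EC2 with EC3 hides a primary DCR result. It does not, because EC3's primary endpoint is safety. SAP 10.1 also calls for adverse event summaries by study part, although it says by treatment as well, and its maximum-severity tables by preferred term use the pooled groups. The two cohorts share the 1:3 ratio and two-week schedule, and the SAP gives a reason for combining them.
- **FEC.** It is reported alone, so the problem does not cover every fixed-dose cohort.
- **Synopsis interval.** The protocol describes expansion cohorts as 10 to 16 subjects with a single tumor type. Its per-expansion-cohort interval is therefore not clearly a promise about DEC2 as a whole.
- **Response criteria.** Protocol 14.3.3 says "Since iRECIST methods were not implemented at the time of dose escalation, DCR for these cohorts will be analyzed per RECIST v1.1". SAP 9 now applies one modified criterion throughout, so differing criteria are no longer an argument against pooling.
- **Tumor types.** A reader might infer that DEC and DEC2 enrolled different tumor types. Those details are in Supplement A, whose clinical text is not available, so this cannot be confirmed.

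**Conclusion.** The point holds as a gap and an unresolved conflict within the plan. SAP 7.1 makes DEC/DEC2 the reporting group, and Table 2 gives only DEC2 a DCR primary endpoint. None of the rules stated in the SAP yields a DEC2-only DCR without an added assumption. The by-cohort and Phase 2 PD-1 analyses in Protocol 14.3.3, which are exploratory there, are not named in the SAP, and SAP 13 does not acknowledge this.

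The actual effect cannot be computed from the documents. For a 20-point difference between the cohorts, the displacement is about 2.4 to 10.9 points under the assumed sizes, and it is zero if the two DCRs are equal. Because the plan reports these rates descriptively, the consequence is a mislabeled or unclear estimate, not a wrong test decision. It is nevertheless more than missing detail: followed as written, the pooling rule reports one cohort's primary endpoint mixed with an escalation cohort.

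**What to change.** Before database lock, amend the SAP as follows:

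1. In SAP 9, name the DEC2-only DCR with its exact 95% Clopper-Pearson interval as the primary analysis for DEC2. Keep the pooled DEC/DEC2 DCR as supportive.
2. Define study part, and state that it is crossed with treatment in the DCR and Grade 3 or higher adverse event tables. This also shows EC3 apart from EC2 on EC3's own primary endpoint, which is safety.
3. Record the pooling of DEC with DEC2 and of EC2 with EC3 in SAP 13.

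Separate overall survival columns are optional, since survival is exploratory in these cohorts. No new data are needed. The cost is an extra column or two, with intervals that will be wide at these sizes (24.7% to 75.3% for 8/16).

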4.2. Primary Objective

The primary objective is to assess the safety and tolerability of multiple IT doses of INT230-6 in subjects with advanced or recurrent malignancies. This will be assessed by the rate of grade 3 or higher adverse events attributed to INT230-6 and not the underlying disease.

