10.2. Clinical Laboratory Evaluations

Clinical laboratory values will be summarized in SI units. Severity grades will be programmatically calculated using standard American Medical Association's (AMA) laboratory normal ranges [AMA Manual of Style, AMA 2009] and the quantitative NCI CTCAE 4.03 criteria (when available for a specific laboratory abnormality). Laboratory values considered to be normal by CTCAE criteria, meaning they do not qualify as Grade 1 - 4, will be assigned a severity grade of 0. For laboratory tests without any CTCAE criteria, toxicity grades will be recorded as 99.

Summary statistics of numerical laboratory test results and changes of test results from baseline will be reported by treatment for hematology, coagulation, serum chemistry, and urinalysis at each scheduled time point. For values with categorical results, the frequency and percentage of each result category will be tabulated at each scheduled time point by treatment. Shift tables will also be included reporting change from baseline category (low, normal, high) to post-dose category (low, normal, high) for cohorts and overall. Abnormal laboratory values that lead to a change in subject management or that are considered to be of clinical significance will be reported as an adverse event (serious adverse event if relevant) and summarized by SOC/PT and according to severity in the appropriate AE tables. Clinical significance will be determined by the Principal Investigator at each site.

Individual test result records, including repeat assessments, and comments for hematology, coagulation, serum chemistry, and urinalysis will be displayed in listings. Laboratory values outside normal limits will be identified with flags for high, low, and normal limits in the listings. Pregnancy test results will be displayed in a listing.

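### SAP 7.1 keeps unscheduled laboratory values out of the shift tables, so an abnormality seen only off schedule and not meeting an adverse event criterion appears only in listings

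*SAP*

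**What the plan says.** SAP 7.1 (General Reporting Conventions) opens its list with a statement of scope: "The following data conventions are applied to all data presentations and summaries". One item in the list reads: "Measurements from unscheduled visits will be included in listings, but not summary tables".

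SAP 10.2 (Clinical Laboratory Evaluations) plans four things that matter here:

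- Numerical results and changes from baseline "will be reported by treatment for hematology, coagulation, serum chemistry, and urinalysis at each scheduled time point". Categorical results are tabulated on the same scheduled basis.
- "Shift tables will also be included reporting change from baseline category (low, normal, high) to post-dose category (low, normal, high) for cohorts and overall".
- CTCAE 4.03 grades calculated by program, although the section specifies no table of worst grade.
- "Individual test result records, including repeat assessments, and comments for hematology, coagulation, serum chemistry, and urinalysis will be displayed in listings".

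The same section gives abnormal values a second route, into the adverse event tables. It is open to values that alter how the subject is managed. It is also open on clinical grounds, since a value "considered to be of clinical significance will be reported as an adverse event (serious adverse event if relevant) and summarized by SOC/PT"; severity is tabulated there too.

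**The concern.** Unscheduled draws are not a random sample of a subject's laboratory values. Many are taken because something looks wrong, so they are more likely to be abnormal than scheduled draws. Leaving them out of by-visit means is normal practice, because they belong to no visit and would distort the column they were put in. A shift table asks a different question: how far did this subject move from baseline at any time after dosing? Removing the draws prompted by illness removes the values most likely to answer it.

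At stake is the laboratory part of the safety picture. Adverse event tables depend on a value meeting a criterion that is partly a matter of investigator judgment, in an open-label, non-randomized study. Laboratory tables do not, and so serve as a cross-check. Of those planned, the shift table is the one that could carry a subject's worst value.

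**Working it through.** No arithmetic reproduces a plan figure here. The check is whether any text brings unscheduled values back into a summary, and where the rule could matter.

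**Step 1: scope.** The SAP 7.1 conventions apply to all presentations and summaries. Neither SAP 10.2 nor SAP Appendix 1 exempts the shift tables. Protocol 14.3.5 plans the same shift tables without excluding unscheduled values, and SAP 13 records no change in method from the protocol.

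**Step 2: direction.** For one subject and one test, let S be the scheduled post-dose values and U the unscheduled ones. The worst value over S and U together is at least as bad as the worst over S alone. So the number of subjects shifted out of normal, counted on S, is never higher than the number counted on S and U. The two are equal only if every subject with an abnormal value in U also has one of the same kind in S. Exclusion can only understate.

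**Step 3: where it can arise.** In Protocol Table 12 (14-day dosing, monotherapy E cohorts) the laboratory visits are:

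| Period | Scheduled laboratory days | Count |
|---|---|---|
| Cycle 1 | 0, 1, 7, 14, 21 | 5 |
| Cycle 2 | 0, 7, 14, 21 | 4 |
| Cycle 3 | 0, 7, 14 | 3 |
| Maintenance | every 9 weeks, ±10 days | 1 per visit |

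Induction has 5 + 4 + 3 = 12 scheduled laboratory visits, mostly 7 days apart. In maintenance the nominal gap is 9 × 7 = 63 days, or 53 to 73 days if the window is applied to the interval. Protocol Table 13 then has laboratory tests at End of Treatment only. An abnormality that arises and resolves inside a 63-day gap can be seen only on an unscheduled draw.

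**Step 4: what the adverse event route recovers.** Protocol 13.1 makes a laboratory abnormality an adverse event if it leads to stopping study drug, needs therapeutic intervention, is clinically significant, is serious, or is assessed as an adverse event by the investigator. SAP 10.2 adds a change in management. An off-schedule value meeting any of these reaches the adverse event tables but is still absent from the shift table. One meeting none of them appears only in listings.

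**Step 5: effect of one subject.** SAP 5 gives 110 enrolled subjects, so one reclassified subject moves an overall percentage by 1/110 = 0.9 points. SAP 7.1 reports four treatment groups. If these were of equal size (an assumption; group sizes are not given), each would hold 110/4 = 27.5 subjects and one subject would be worth 1/27.5 = 3.6 points. How many subjects would be reclassified is not in the documents.

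**The case against.** The strongest reply is that SAP 10.2 never says the shift is to the worst post-baseline value. The sentence follows two on by-time-point summaries, so a by-visit shift is a natural reading, and excluding unscheduled values would then be conventional. The table shells that fix the layout are a companion document outside this text. SAP 7.1 also defines post-baseline by time alone, not by visit type. This part stands: the layout is open. It does not remove the point. If the shift is overall, the rule biases it; if it is by visit, no planned laboratory table shows a subject's worst value at all.

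The second reply is mitigation, and most of it stands. Listings keep every value, with flags for results outside normal limits. Induction, when dosing is most frequent, is sampled closely. A draw taken for illness and acted on will usually become an adverse event.

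A reader might go further in four directions that the documents do not support:

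- **That only values judged clinically significant return as adverse events.** Protocol 13.1 and SAP 10.2 list several other criteria.
- **That the categorical laboratory tables are biased too.** SAP 10.2 ties them to scheduled time points, where the exclusion is appropriate.
- **That unscheduled scans are lost from response or progression.** SAP 9.2 and Appendix 1 take progression from recorded clinical or radiographic deterioration, and PFS is listed only. Best response is derived per subject, and nothing says that off-schedule scans are left out of it.
- **That almost all toxicity between maintenance visits goes uncounted.** Adverse events are collected whatever the visit type, and an abnormality that persists is seen at the next visit.

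**Conclusion.** The point holds in a limited form. As written, SAP 7.1 keeps unscheduled laboratory values out of the SAP 10.2 shift tables, and those tables lean towards normal to an unknown extent. The values that reach no table at all are abnormalities seen only off schedule that met no adverse event criterion.

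A reader might infer that the primary safety result is biased. It is not: Protocol 4.2 says "This will be assessed by the rate of grade 3 or higher adverse events attributed to INT230-6 and not the underlying disease", and SAP 10.1 counts events whatever visit they are linked to. For DEC2 and FEC, SAP Table 2 makes disease control rate the primary endpoint, so safety as the primary aim describes the trial overall, the monotherapy cohorts and DEC.

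A reader might also infer a breach of Protocol 13.1, which promises that abnormal values will be graded and reported. Listings in the study report can meet that promise. What is missing is a summary.

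The conclusion assumes that the SAP 7.1 rule is applied literally and that the unseen table shells make no exception. The maintenance example rests on Table 12, which covers the monotherapy E cohorts; the combination schedules are not in the text available.

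**What to change.** - Reword the SAP 7.1 sentence so that it applies to by-visit summaries only, including categorical results by scheduled time point.
- State in SAP 10.2 that the overall shift table uses the worst post-baseline value from scheduled and unscheduled draws. Because low and high are opposite directions, take the lowest value for shifts to low and the highest for shifts to high, so that a subject with both is counted in both.
- Add a shift from baseline grade to worst post-baseline CTCAE grade. The grades are already to be calculated, and low/normal/high alone does not show severity. Leave out tests without CTCAE criteria, which SAP 10.2 codes as 99.
- Record the change in SAP 13.

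No new data are needed, since the individual and repeat results are already to be listed. The cost is two or three SAP sentences, a flag in the analysis data and one extra table. Abnormality counts may rise, so a footnote should say that the table includes unscheduled draws, many of them taken because a problem was suspected.
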